Approximately 200 women from up to 5 mobile units who screen positive on VIA will be enrolled.

First, we anticipate that we will need to consent and screen for eligibility approximately 2,000 women getting cancer screening at La Liga mobile units in order to enroll approximately 200 women who screen positive on their VIA screening and who have consented. This estimate is based on current VIA positivity rates of approximately 10%.

Women who consent may complete the following study activities:

Activity 1: Allow mIVAA to be used as part of VIA for cervical cancer screening.

Activity 2: Complete a survey. The survey will include:

- Socio-demographic characteristics, reproductive and clinical history, knowledge of cervical cancer, social support, household decision making, experience with screening, barriers and facilitators to attending follow-up clinical evaluations, mobile phone use and feedback on the intervention.

- Contact information (including primary and back-up mobile phone numbers) will be collected in addition to information on mobile phone ownership and use.

The survey will be administered electronically, or on paper if not available electronically, by a trained data collector using Qualtrics, REDCap or another offline app based on a mobile device. Surveys will be conducted in Spanish. Surveys may include open-ended questions that may be audio recorded, transcribed and translated to English for analysis and inclusion in any publications.

Activity 3: Allow review of medical records to assess follow-up and correlates of follow-up.

Activity 4: Complete a few questions about motivators or barriers to follow-up clinical evaluation.

The interview will be conducted by phone or in person and will administered electronically, or on paper if not available electronically, by a trained data collector using Qualtrics, REDCap or another offline app based on a mobile device. Surveys will be conducted in Spanish. The interview will include open-ended questions that may be audio recorded, transcribed and translated to English for analysis and inclusion in any publications.

Study activities with enrolled La Liga health providers:

- The same providers and administrative staff who enrolled for aim 1 will continue with activities for aim 2. We will conduct a training/orientation to inform them of any changes to mIVAA and inform them of the flow of research activities for aim 2.

Midwives with assistance from nurse technicians

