Activity 2: Provide feedback on the use of mIVAA through a survey, brief interviews, and/or an individual or group interview. Discussions will assess feedback and satisfaction with the mIVAA system.

Study staff will document in Spanish La Liga provider and staff feedback, and translate to English for analysis and inclusion in any publications. Interviews may be audio recorded, transcribed and translated.

Medical record abstraction for historical controls

For the control group, data from 200 women who received cervical cancer screening at a mobile unit prior to use of mIVAA will be abstracted from medical records to assess follow-up and correlates of follow-up.

6. Selection of Subjects:

The following groups of participants will be included in the study:

1. Health providers (for aim 1 & 2): Approximately 18 health providers and administrative staff identified in consultation with La Liga will participate in the study, based on the following eligibility criteria.

Inclusion criteria:

- Age 18 or older
- Must be a health provider (Midwives, nurse technicians, expert colposcopists, etc.) or administrative staff working in La Liga clinics and/or staffing the mobile units.
- Agree to be audio recorded

Exclusion criteria:

- Does not understand the study purpose and details
- Is not willing to sign an informed consent

2. Women for Aim 1: Approximately 102 women who are screened for cervical cancer in the mobile units will be approached for participation in the study, based on the following eligibility criteria.

Inclusion criteria:

- Age 18 or older
- Patients coming to the mobile unit for cervical cancer screening
- Willing to allow use of mIVAA during screening with VIA
- Agree to be audio recorded

Exclusion criteria:

- Currently pregnant
- History of hysterectomy
- Does not understand the study purpose and details
- Is not willing to sign an informed consent

3. Women for Aim 2: Approximately 2,000 women will be approached for participation and consented to allow eligibility screening (eligibility criteria listed below) for participation in the study. Approximately 200 women who screen VIA+ will continue their participation in the study.

Inclusion criteria:

- Age 18 or older
- Patients coming to the mobile unit for cervical cancer screening
- Screen-positive on the VIA
- Willing to allow use of mIVAA during screening with VIA
- Agree to be audio recorded

Exclusion criteria:

- Currently pregnant
- History of hysterectomy

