To minimize the possibility of coercion or undue influence, participants will be informed of all aspects of the study and questions will be answered. The voluntary nature of the study will be emphasized and that the participant may withdraw at any time for any reason. Women getting cancer screening who are being consented will be told that their decision to accept or decline participation in the study will not impact their ability to receive health services provided by La Liga. Health providers and administrative staff

who are being consented will be assured that there will be no penalty or impact on their employment if they refuse to answer and/or skip any questions in the interviews.

Historical controls: For women whose records are used as a historical control, we will be unable to conduct informed consent. We will request a waiver of consent from the Duke IRB, as is required by Duke.

10. Risk/Benefit Assessment:

Risks:

There are three potential risks of the study: loss of confidentiality, discomfort with questions, and, for women at mobile units only, the unlikely risk associated with placing the Pocket, a digital image capture device, within the vaginal canal.

Loss of confidentiality

There is always risk associated with loss of confidentiality for participants in a study. However, this risk of loss of confidentiality will be minimized through rigorous training of study personnel, use of study identifiers to make data de-identified unless linked to personal identifiers, restricting access to identifiable data, and publishing only aggregate (not individual-level) statistical summaries that limit re-identification of participants.

Discomfort with questions

There is also the possibility that some questions might upset or create discomfort in participants if topics are considered sensitive. Women at mobile units may be upset by questions about personal experiences with cervical cancer screening and their belief about procedures. Research staff will look for signs of discomfort and assure participants that they are not being judged, that answers will be kept confidential, and that they can refuse to answer any question.

Physical risks

For La Liga health providers and administrative staff there are no physical risks from participation in the study.

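### Agreement to audio recording is an entry requirement for Aim 2 women that the primary outcome does not need and the historical controls do not face: an avoidable, probably small, one-sided filter

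*Combined protocol and SAP*

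**What the plan says.** Section 6 (Selection of Subjects) lists "Agree to be audio recorded" as an inclusion criterion for Aim 2 women. The same line appears for Aim 1 women and for providers.

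Section 5 (Design & Procedures, Aim 2) uses permissive wording. On the survey: "Surveys may include open-ended questions that may be audio recorded, transcribed and translated to English". On the later interview: "The interview will include open-ended questions that may be audio recorded, transcribed and translated to English for analysis and inclusion in any publications". Both are administered by a trained data collector, electronically or on paper. Section 14 (Privacy, Data Storage & Confidentiality) is firmer. In a list of safeguards it says, without qualification, that interviews will be recorded on encrypted devices.

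Follow-up in the mIVAA arm comes from charts, under the activity "Allow review of medical records to assess follow-up and correlates of follow-up". For the controls, "data from 200 women who received cervical cancer screening at a mobile unit prior to use of mIVAA will be abstracted from medical records". Section 9 adds: "For women whose records are used as a historical control, we will be unable to conduct informed consent". No recording criterion is stated for them.

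Section 12 names loss to follow-up among referred women, intervention versus control, as the primary outcome. It estimates the effect as a difference in attendance proportions and states no adjustment of that comparison for selection.

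**The concern.** Aim 2 compares prospectively enrolled women with historical charts, so any entry condition applied only to the prospective arm can shift the contrast. Some conditions, such as consent and acceptance of mIVAA imaging, come with the design. Willingness to be recorded does not: a woman who declines it could still be screened, imaged, referred and followed through her chart.

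If willingness to be recorded is related to attendance, excluding decliners changes usual-care attendance in the mIVAA arm before mIVAA has any effect. The analysis could not recover this. Section 7 logs reasons for ineligibility or refusal only when women offer them, and no outcomes are planned for women who are excluded. The criterion also removes VIA+ women from a recruitment estimate that allows only for the positivity rate.

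**Working it through.** **Inputs from the documents.** 200 women per group, 13.5-point difference, 80% power, 5% level, odds ratio about 1.8, standardised effect about 28% (section 12). 77% of referred women do not attend, so 23% do (section 4). About 2,000 women consented at about 10% VIA positivity to enrol 200 (section 5).

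**Assumptions.** r is the share of otherwise eligible VIA+ women who decline recording, and q is their attendance. The documents give neither. I take r from 5% to 20% and vary q. Tests are taken as two-sided, since the plan does not say.

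**The plan's own figure.** The detectable standardised effect at 200 per group is (1.960 + 0.842) x sqrt(2/200) = 0.280, matching the stated 28%. A comparison of 70% with 56.5% needs 200 per group and has an odds ratio of 1.80. At the documented 77% against 63.5%, power with 200 per group is 84.2%. No sample-size figure is in dispute.

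**Shift with no true effect.** Attendance among women who remain is (0.23 - r x q)/(1 - r). Subtracting 0.23 gives shift = r x (0.23 - q)/(1 - r).

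| q | r = 5% | r = 10% | r = 20% |
|---|---|---|---|
| 0% | +1.2 points | +2.6 | +5.8 |
| 10% | +0.7 | +1.4 | +3.3 |
| 23% | 0 | 0 | 0 |
| 36% | -0.7 | -1.4 | -3.3 |

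Example: r = 20%, q = 10% gives 0.20 x 0.13/0.80 = 0.0325. The 36% row mirrors the 10% row (23 + 13 instead of 23 - 13) and shows that the sign can reverse.

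**Set against the target.** For the filter alone to produce 13.5 points, r = 0.135/(0.365 - q). That is 37% declining with none of them attending, or 51% declining with 10% attending.

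**Recruitment.** Women needed = 200/(0.10 x (1 - r)): 2,106 at r = 5% and 2,500 at r = 20%. If recruitment stopped at 2,000, enrolment would be 2,000 x 0.10 x (1 - r), or 190 and 160. Power for 77% against 63.5% with 200 controls would then be 83.3% and 80.0%.

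**The case against.** **Recording may not be optional for the woman.** The permissive wording may give discretion to the study team only. Nothing says that she may decline and stay enrolled, section 14 reads as if interviews are always recorded, and the consent form is not in the text available. The line "Women who consent may complete the following study activities" does not settle this, because it also covers imaging and record review. This stands in part. A reader might infer a plain contradiction, required at entry yet optional in practice. The documents do not support that, but they do leave sections 5 and 14 to be reconciled.

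**The qualitative work needs recordings.** Section 12 plans thematic analysis of transcripts, with 20% double-coded, and uses interviews with women to assess satisfaction and barriers. That is a real use for audio. It does not justify exclusion from the whole study: answers are already taken electronically or on paper, and section 10 lets women refuse any question. A woman may therefore leave every open question unanswered and remain enrolled, yet is barred for declining to have answers recorded.

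**The bias is hypothetical, small and shared with other filters.** This stands. Women averse to recording may overlap with those who refuse consent or imaging, so the added effect may be smaller than the table shows.

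**Refusals are logged, and the recruitment cost is slight.** Section 12 reports the percentages consenting and refusing, which shows part of the exclusion but no outcomes for those excluded. Staff describe eligibility before individual consent, so some women would decline before signing. That raises the number approached rather than the number consented. At 200-800 women a month in each of five units (1,000-4,000 in all), 106-500 more women is a modest load.

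**Conclusion.** A minor point that holds. The criterion is an avoidable exclusion, applied to one arm only, that the primary outcome does not need.

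A reader might infer that it inflates attendance with mIVAA. The documents do not support that: with 5-20% declining, the shift is zero if decliners attend at 23%, +0.7 to +3.3 points if they attend at 10%, and negative if they attend more often than 23%. Nor do they support the inference that the filter could account for the target effect, given the 37-51% refusal shares that this would take. The refusal share and the decliners' attendance are assumptions throughout.

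The bias argument does not reach Aim 1, a pilot with no historical comparison. Removing the criterion also leaves the larger difference between the arms in place: consented women who accept mIVAA against charts used without consent.

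**What to change.** - Delete the recording criterion for Aim 2 women in section 6.
- Make audio recording a separate opt-in on the consent form, with written notes for women who decline.
- Report how many VIA+ women decline recording. Because they stay enrolled, their follow-up is read from records and their attendance can be set beside that of the others, which replaces the assumed r and q with data.
- Reconcile section 14 (interviews recorded) with section 5 (may be recorded), and say whose interviews section 14 means.
- Aim 1 may be changed for consistency. The provider criterion can stay.

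The cost is a change of wording in the eligibility criteria and consent form, and fewer verbatim transcripts for the thematic analysis. Sample size, outcome and planned comparison are unchanged.

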Cervical cancer screening standard of care:

La Liga mobile units are set up close to busy locations (e.g., a market) in pre-selected communities. Screening is offered 9 am-3:00 pm every weekday for 1-2 weeks per community. Women receive Pap, VIA, breast, thyroid and rectal exams and each clinical encounter typically lasts 15 min (see Table 1). La Liga also has two central administrative offices and clinics (detection centers) where cancer-related screening and treatment is offered by health providers including expert colposcopists, and where administrative staff are based. Training has been conducted on use and reprocessing of the Pocket device, however it is not currently in use in clinics.

Currently, if VIA+ (any evidence of whitening after application of acetic acid; determined at the same time as the exam), women are advised during screening that follow-up clinical evaluation with a medical expert (colposcopist) is required, however no referrals for care are made until Pap smear results are received in about 30 days, unless there is a suspicion of cancer. Patient information and the diagnosis is entered into an electronic database at La Liga (WebLiga). La Liga staff contact women who screen positive and are diagnosed with cervical cancer or pre-cancer to schedule follow-up appointments for care, management and treatment. If the woman misses the colposcopy appointment, La Liga staff call to reschedule. After three attempts at rescheduling, the woman is considered lost-to-follow-up.

Table 1: Standard of care and proposed intervention (mIVAA)

Standard of care	mIVAA
Screen with VIA (IVAA) and Pap in MUs	Screen with VIA, Pap and mIVAA (digital imaging device component) in MUs
No expert review	Expert reviews digital images of the cervix remotely using mIVAA's telemedicine component and refers for follow-up appointments for care, management and treatment, if positive
Refer women for colposcopy based on Pap results 3-4 weeks later	For any women not referred already, refer if needed based on Pap results, per standard of care

Perform diagnostic colposcopy and biopsy and treat, if possible, at central La Liga clinic in Lima	Perform confirmatory colposcopy and biopsy and treat, if possible, at central La Liga clinic in Lima
Additional visits to complete treatment, per standard of care.	Additional visits to complete treatment, per standard of care.

Description of intervention and framework for development:

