Activity 2: Provide feedback on the use of mIVAA through a survey, brief interviews, and/or an individual or group interview. Discussions will assess feedback and satisfaction with the mIVAA system. Individual or group interviews may be completed in person, by phone or by Zoom. The interviews will be audio recorded using an encrypted digital audio recorder, voice recording app on tablet or using Zoom's audio recording function.

Study staff will document in Spanish La Liga provider and staff feedback, and translate to English for analysis and inclusion in any publications. Interviews may be audio recorded, transcribed and translated.

Aim 2: To evaluate effectiveness of mIVAA by comparing the attendance for follow-up clinical evaluation among women screened with mIVAA compared to historical data on women referred for follow-up without mIVAA.

Hypothesis: Use of mIVAA will result in a 13.5% increase in the proportion of screen-positive women completing follow-up clinical evaluation, compared to situations where mIVAA is not used.

Methodology:

For this aim, we will enroll approximately 200 VIA+ women attending any one of five La Liga mobile units for cancer screening, and approximately 18 La Liga health providers and administrative staff. As per standard of care, VIA+ women would be referred for follow-up care. Improving attendance of follow-up care is a primary objective of the study.

As part of the evaluation, we will:

- Assess mIVAA for image quality, network stability, challenges with image transmission, ability and time to reach experts and receive feedback from experts (two-way communication between health providers).
- Assess provider feedback and satisfaction from the use of mIVAA
- Document timing of providing women who screen positive on VIA with colposcopist evaluation of cervical images and management plans based on digital cervical images, and follow-up appointment for confirmatory colposcopy and biopsy.
- Collect survey data from women to identify correlates of follow-up.
- Document rate of follow-up care among women who are referred for management and treatment.
- Abstract historical data from medical records including: clinical notes on Pap results; for women who screened positive on VIA, rates of attending follow-up appointments and colposcopist evaluation; and possible reasons for not attending follow-up appointments.

Study activities with enrolled women

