Prior to signing, participants will be given the opportunity to ask questions and have them answered to their satisfaction. They will be encouraged to take the time they need to consider study participation and to ask questions.

Women seeking cancer screening will be recruited on the same day as they come to the mobile unit and will need to be consented prior to their exam with the midwife. Therefore, in practical terms women will have limited time to consider their study participation. They will be encouraged to take the time they need and to ask questions. This protocol is necessary such that the midwife can use mIVAA at the time of the woman's cervical cancer screening. The midwife will only obtain images with mIVAA from women who have provided consent.

Part 3 - Acquire consent with a signature from the participant

Written consent will be obtained from all study participants prior to any study participation, including eligibility screening. Only those participants providing written informed consent will be enrolled in the study. For aim 2, the majority of the 2,000 women consented will not be eligible (VIA negative) and therefore will not continue their participation past the eligibility screening. Participants who are illiterate and those with minimal literacy will have the Spanish consent form verbally summarized by the study staff. The participant will provide their thumbprint on the consent. A literate witness will be asked to observe the consent form discussion and sign the consent form.

A signed copy of the consent form will be given to study participants. Participants will have contact information for the principal investigator, the study coordinator and the ethics board to contact in the event of any question or concern. A second signed copy of the signed consent will be scanned and stored electronically in research records, then saved in the patient's medical record at La Liga. Research staff will document the study consent in the medical record for each La Liga patient who is enrolled in the study. The consent form may be stored in the paper medical record at La Liga. Consent records will be maintained by La Liga.

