etc.). The difference in the proportion of women attending follow-up clinical visits between the two arms will be calculated to estimate the intervention effect at 5% level of significance level. Baseline covariates will be modeled using multivariable logistic regression to determine patient characteristics associated with loss-to-follow-up. Measures of predictive power (like R-square) and goodness of fit tests (like the Pearson chi-square) will be used to assess the fit of the regression model.

As part of the qualitative analysis plan, we will conduct applied thematic analysis on the observation notes and interview transcripts. Electronic files will be uploaded into QSR NVivo--software that supports coding and finer level re-coding of text data that enables researchers to explore how concepts fit by developing and modifying a hierarchical coding index. Thematic analysis will be conducted via an iterative process of data collection and analysis that utilizes four interrelated steps: reading; coding; data display; and data reduction. The team will use a codebook of a priori, structural codes based on the interview guide, and then a second round of coding, i.e. content coding, will be conducted to identify additional themes, ideas, or concepts. Twenty percent of transcripts will be coded by 2 team members, inter-rater reliability assessed, and discussions held to resolve coding discrepancies. We will create a summary of each interview and look across interviews for commonly named problems and solutions for each step of image acquisition, transfer, and interpretation.

Data will be summarized in the following areas: Core functionality (including expectations, and communication formats), data analytics, storage and availability, (3) Security, hosting and privacy, 4) Mobile delivery platform, 5) Monitoring and maintenance, 6) Hardware, equipment, power and connectivity needs.

In interviews with women in aim 1 and 2, we will assess satisfaction with the (a) overall experience, (b) timeliness of evaluation of cervical images and management, and (c) any barriers to attending future clinical visits.

Evaluation outcomes are summarized in table below.

Primary outcome - Efficacy

- Percentage of referred women who are lost to follow-up in intervention versus control arm

Secondary outcomes - Process

- Percentage of women approached who consented to participate in study
- Percentage of women approached who refused to participate in study

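### The only stated estimate of the mIVAA effect is a crude difference between a consented cohort and earlier records; the plan should commit to an arm effect adjusted for record-based covariates and acknowledge clustering

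*Combined protocol and SAP*

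**What the plan says.** All references are to the combined protocol and SAP.

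- **Effect estimate.** Section 12, Statistical analysis plan: "The difference in the proportion of women attending follow-up clinical visits between the two arms will be calculated to estimate the intervention effect", at the 5% level. No adjustment, matching, weighting or standardisation is described.
- **Regression.** The next sentence reads: "Baseline covariates will be modeled using multivariable logistic regression to determine patient characteristics associated with loss-to-follow-up". Sections 2 and 3 likewise present the multivariable modelling as a study of correlates. Arm is neither named as a term nor excluded.
- **Primary outcome.** Section 12 lists it under an efficacy label: "Percentage of referred women who are lost to follow-up in intervention versus control arm".
- **mIVAA arm.** Section 9: "Only those participants providing written informed consent will be enrolled in the study".
- **Control arm.** Section 5, Medical record abstraction for historical controls: "data from 200 women who received cervical cancer screening at a mobile unit prior to use of mIVAA will be abstracted from medical records". The stated purpose covers follow-up and its correlates. Section 9 says that consent cannot be obtained for these women and that a waiver will be requested.
- **Data abstracted for controls.** Section 5, Aim 2: "Abstract historical data from medical records including: clinical notes on Pap results", followed by attendance, colposcopist evaluation and possible reasons for not attending. Age, mobile unit, community and screening date are not named.
- **Setting.** Section 5 draws Aim 2 women from up to five mobile units and, under standard of care, says: "Screening is offered 9 am-3:00 pm every weekday for 1-2 weeks per community". Neither the sample size paragraph nor the analysis plan mentions clustering.

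**The concern.** Aim 2 sets out to evaluate effectiveness against historical data. Women who agreed to join a study on the day of screening may differ from an unselected set of earlier records in age, district or other characteristics related to attendance. A crude difference adds any such imbalance to the effect of mIVAA, and nothing in the stated analysis separates the two. The plan already contains a logistic model that could do this for measured characteristics, but does not commit it to that job.

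The secondary concern is precision. Women screened at the same stop share a place, a midwife and a journey to the detection centre, so their attendance may be correlated. A test or interval that treats them as independent may then reject too often or be too narrow.

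**Working it through.** **1. The plan's own sample size.** Section 12 states 200 per group, a 13.5-point difference, 80% power, 5% level, an odds ratio of about 1.8 and an effect size of about 28%. The base rate is not stated. Trying 70% v 56.5% loss, two-sided, without continuity correction:

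- n = [1.96·√(2·0.6325·0.3675) + 0.842·√(0.70·0.30 + 0.565·0.435)]² / 0.135² = 199.03, rounded up to 200 per group; power at 200 is 80.2%.
- Odds ratio = (0.70·0.435)/(0.30·0.565) = 1.80; Cohen's h = 0.281.

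All the stated figures reproduce, as a comparison of independent proportions with no design effect. At the 77% loss quoted in Section 4 (77% v 63.5%), power would be 84.2% and the odds ratio 1.92. The clustering figures below therefore start from 70% v 56.5%.

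**2. Case-mix illustration (all values assumed).** Suppose mIVAA has no effect. A binary factor carries 35% attendance when present and 15% when absent, and is present in 40% of controls and 60% or 70% of mIVAA women.

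- Controls: 0.40·35 + 0.60·15 = 23% (which equals 100 − 77).
- mIVAA, 60% prevalence: 0.60·35 + 0.40·15 = 27%, a spurious 4 points.
- mIVAA, 70% prevalence: 0.70·35 + 0.30·15 = 29%, a spurious 6 points.

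With 200 per arm and a pooled z-test at two-sided 5%, P(p<0.05) = Φ[(d − 1.96·SE₀)/SE₁]:

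- 4 points: Φ[(0.04 − 1.96·0.0433)/0.0433], about 15%.
- 6 points: Φ[(0.06 − 1.96·0.0439)/0.0438], about 28%.

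**3. Women per stop.** Low: Section 4's 200 women per unit per month gives 200/4.33 × 10% = 4.6 VIA-positive women in a one-week stop, taken as 5. High: Section 5 says that "each clinical encounter typically lasts 15 min", so one midwife over six hours does 24 exams a day; × 10 weekdays × 10% = 24. The high figure is a ceiling in the mIVAA arm, where only consenting women count. It implies 200/24, or about 8 stops; the low figure implies 200/5 = 40.

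**4. Clustering illustration (ICC assumed; the documents give none).** Design effect DE = 1 + (m − 1)·ICC. The documents do not say how control records are spread over stops, so both cases are shown. Type I error of a test that ignores clustering is 2[1 − Φ(1.96/√k)], with k = (1 + DE)/2 if only the mIVAA arm is clustered and k = DE if both are. Power multiplies each clustered arm's variance by DE, at 70% v 56.5%.

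| m | ICC | DE | Type I, mIVAA arm only / both | Power, mIVAA arm only / both |
|---|---|---|---|---|
| 5 | 0.01 | 1.04 | 5.2% / 5.5% | 79% / 79% |
| 5 | 0.05 | 1.20 | 6.2% / 7.4% | 76% / 73% |
| 24 | 0.01 | 1.23 | 6.3% / 7.7% | 76% / 72% |
| 24 | 0.05 | 2.15 | 11.8% / 18.1% | 61% / 48% |

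These treat stops as independent between arms. If the same units serve both periods and their effects are stable, part of the unit effect cancels and the loss is smaller.

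**The case against.** The strongest reply is that this is a gap in wording rather than a wrong analysis. The design is declared observational, and the abstract speaks of feasibility and preliminary impact. Control records are abstracted for correlates as well as follow-up, so a pooled model containing arm would fit the text. This stands in part: a reader might infer that arm is left out of the model, and the documents do not support that. They simply do not say. But Aim 2 claims effectiveness, the outcome carries an efficacy label, and the only quantity assigned to the intervention effect is the crude difference.

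A second reply is that adjustment cannot repair a historical comparison. That also stands. For example, a 5-point secular drift from 77% to 72% loss with no true effect would give p<0.05 in about 21% of studies, and adjusting for age or district would not remove it unless the drift ran through those variables. A reader might infer that an adjusted estimate makes the arms comparable; it does so only for what is measured in both.

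Third, no passage shows that age or district differs between the arms or predicts attendance, and every ICC here is assumed. A reader might take the bottom row of the table as the expected loss, or conclude that 200 per group is wrong. Neither is supported: that row needs a fully booked midwife for ten days and the highest assumed ICC, and the sample size reproduces on its own terms.

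**Conclusion.** The point holds as a cheap improvement. The plan's only effect estimate is crude, in a design where neither randomisation nor concurrency balances the arms, and the model that could adjust it is not committed to that purpose. The 4 to 6 point bias is illustrative and depends on the assumed prevalences and attendance rates; the case for adjusting does not depend on those particular values.

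Clustering is secondary. For ICC 0.01 to 0.05 and 5 to 24 women per stop, its effect is modest in three of the four combinations (type I error about 5% to 8%, power about 72% to 79%) and large only at 24 per stop with ICC 0.05 (about 12% to 18%, and 48% to 61%). The sample size contains no arithmetic error; it rests on independence, which the plan does not state.

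**What to change.** **Section 12, Statistical analysis plan.** State that the logistic model pools both arms and includes arm, age and, where both arms contain women from the same units or districts, a unit or grouped district term. No passage guarantees that overlap, so check it first. Report the adjusted arm effect as a risk difference with 95% CI beside the crude difference, and base the mIVAA conclusion on the adjusted estimate. As a sensitivity analysis, give an interval that allows for community stop, using a t reference with degrees of freedom from the number of stops in whichever arm or arms are clustered. In a simulation with 8 stops per arm and ICC 0.05, cluster-robust type I error was 7.2% with a normal reference and 5.1% with t on 14 degrees of freedom. Keep survey covariates for a mIVAA-only correlates model, because controls have no survey.

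**Section 5, Aim 2.** Add age, unit, community and screening date to the historical abstraction list, after checking that the records hold them.

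**Section 12, Sample size justification.** Say that the 80% power assumes independent women.

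**Cost.** A few lines, a little more abstraction and probably a wider interval. The model is affordable: if all 400 women are referred, attenders number 0.23·400 = 92 to 0.23·200 + 0.365·200 = 119. If only 100 mIVAA women are referred (assumed), they number 0.23·300 = 69 to 0.23·200 + 0.365·100 = 82.5. With arm, age and four unit terms that is still at least 69/6 = 11.5 attenders per term.

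Time trends, consent selection and the differing make-up of the referred women in the two arms are not removed and should be stated as limitations.
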